5.3 Informed Consent Procedures

If a potential subject expresses interest in learning more about the study, a study staff member will speak to the potential subject in a private area and review the consent form. The potential subject will be encouraged to ask questions regarding the study. At the end of the discussion, potential subject will be given the opportunity to sign consent in order to participate in the study or to decline participation. Potential subjects may also take the consent form home and think about whether or not they wish to participate, however, this may mean that the provider will delay changing their medications until they decide whether or not to participate. In order to minimize any undue pressure or appearance of coercion, a subject's provider will not be the one obtaining informed consent and the consenting process will occur in a location separate from the provider.

All individuals obtaining informed consent will be trained to protect PHI and will be trained by the PI to obtain and document informed consent.

Subjects with a legally authorized representative who are not competent to sign consent will not be allowed into the study.

During the consenting process, potential participants will also be given the opportunity to consent to have their data entered into the mental health repository (MIRB#: 00696) and stored indefinitely. This will be handled with a separate consent. Participants do not have to sign this additional consent to participate.

5.4 Inclusion/Exclusion Criteria

Inclusion Criteria

1. Currently receiving outpatient treatment for a mental health diagnosis within the VA Puget Sound Health Care System from a provider who is a sub-investigator on this study.
2. Currently experiencing a sub-optimal medication response as assessed by either continued symptoms or medication side effects, which in the opinion of their treating provider would indicate a change in medications would be warranted.
3. Currently prescribed polypharmacy, as defined as five or more medications, with at least two being for a mental health diagnosis. Also allowable would be one medication for a mental health diagnosis and another medication for side effects related to a medication prescribed for the mental health diagnosis.
4. Between the ages of 18 and 75.

Exclusion Criteria

1. Any mental or physical health diagnosis, which in the opinion of their treating prescriber would prevent them from being compliant on a medication regimen or being able to complete the study measures.
2. Current/active diagnosis of severe alcohol or drug use disorder.
3. Serious medical or mental health symptoms requiring immediate stabilization and/or hospitalization.
4. Impaired decision making capacity that in the clinical judgement of their provider would affect their ability to provide informed consent.
5. Self-identification as being currently pregnant.

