5.5 Study Evaluations

Measures:

The primary measure to determine clinical effectiveness is the Clinical Global Improvement Scale. This scale will be completed both by the provider and the study coordinator (or study personnel collecting the assessment measures).

The number of medications and treatment utilization will be collected by chart review of the subject's medical record at baseline and at 12 weeks to determine any change in the number and type of medications prescribed.

Any differences between the initial medication plan developed by the provider prior to receiving the pharmacogenetic assay results, the medication optimization plan developed by the provider after the use of the G-DIG tool, and actual clinical practice will be noted. The number and cost of medication changes will also be evaluated.

Participant assessments administered at baseline, 6 and 12 weeks will include measures from the Behavioral Health Lab (BHL; Oslin et al., 2006). These measures will include a demographic questionnaire, GAD-7 (Anxiety), PHQ-9 (Depression), PCL-5 (PTSD), Insomnia Severity Index, Chronic Pain, Screening for Alcohol and Drug use, RAND Health Survey, and Side Effects and Adherence (See Appendix A). The results of the BHL assessments will be placed into the subject's medical record. Participants will also be asked about smoking.

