5.6 Data Analysis

Analysis Plan and Power Calculations: The primary and secondary hypotheses will be calculated using within group t-tests using the Statistical Package for the Social Sciences (SPSS). A statistical power analysis was performed for sample size estimation. The effect size was estimated to be medium (0.50) using Cohen's (1988) criteria. With an alpha = .05 and power = 0.80, the projected sample size needed with this effect size is approximately N = 34 to conduct a single sample t-test. Thus, our proposed sample size of N = 50 should be more than adequate to analyze the main hypothesis for this study and should also allow for expected attrition and the analysis of our secondary hypotheses.

Interpretation: Interpretation of these hypotheses should demonstrate whether the Genecept® Assay and the G-DIG tool are beneficial to Veteran prescribed polypharmacy in order to reduce polypharmacy and improve clinical symptoms. The primary limitation to this study is that there is no control group, so attribution of any change to the pharmacogenetic assay should be done with reservations. If this study shows promising results, future studies should include a randomized control group. Another limitation is sample size. Though with our estimated effect size, we should have power to detect significance, larger sample sizes are preferred to increase generalizability to a larger population.

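### Medication changes ordered before consent are not identified at baseline, so the within-group tests count them in the 12-week change in drug count and symptoms

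*Combined protocol and SAP*

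**What the plan says.** Entry under 5.4 rests on a present state. The patient must be "Currently experiencing a sub-optimal medication response as assessed by either continued symptoms or medication side effects", the treating provider must think a medication change is warranted, and at least five drugs must be currently prescribed. In the text available for review, neither 5.4 nor the sections on design, recruitment and consent ask for recent starts, dose changes, stops or tapers.

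The drug count comes from 5.5: "The number of medications and treatment utilization will be collected by chart review of the subject's medical record at baseline and at 12 weeks". In 5.6, "The primary and secondary hypotheses will be calculated using within group t-tests".

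Three provisions bear on the point:

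- Section 5.1 has the provider write an initial medication plan before seeing the assay results. Section 5.5 says that differences between this plan, the revised plan and actual practice are noted.
- Section 5.3 says that a provider may hold back a medication change while a patient thinks about consenting.
- Section 5.6 states that "there is no control group, so attribution of any change to the pharmacogenetic assay should be done with reservations".

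**The concern.** A pre/post comparison measures everything that happens between the two readings. Here some of that may have been decided before the assay was offered. Patients are recruited by their own prescriber at a visit where a change is thought warranted, so some may already be part-way through one.

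Three cases matter:

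- A drug being tapered at consent is still on the baseline list and gone at week 12. It counts as a reduction under hypothesis 1 (polypharmacy).
- A drug ordered before consent but not yet listed at baseline appears at week 12. It counts as an increase under hypothesis 1.
- A drug started shortly before baseline may show its benefit only afterwards. That counts as improvement under hypotheses 3 (CGI) and 5 (anxiety, depression, quality of life).

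A drug already off the list at baseline does not enter the change in count.

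At stake is whether a significant change can be read as bearing on the assay and G-DIG. Most time-related bias cannot be separated without a control group. This part can, because the chart holds the order dates.

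**Working it through.** **Inputs from the protocol (5.6).** Alpha .05, power 0.80, effect size 0.50, single-sample t-test, stated N = 34, planned N = 50. Sidedness is not stated.

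**Reproducing the plan's figure.** For a one-sample t-test the noncentrality is d × √n, with n − 1 degrees of freedom. With d = 0.50 and two-sided .05, power is .795 at n = 33 and .808 at n = 34. The stated N = 34 is therefore correct as a two-sided calculation. At n = 50, power is .934. The sample size is not in dispute.

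**Inputs that the documents do not give (assumed).** These are the share of participants with a change under way, the SD of the change in drug count, and the response still to come from a recently started drug.

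**Hypothesis 1.** Let q be the share with one listed drug already being stopped, a the share with one addition already ordered, and s the SD of change in drugs. With no assay effect, the standardised mean change is

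d0 = (q − a) / s.

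The chance of p < .05 is the power of the same t-test at d0. With N = 50 and a = 0:

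| q | s | d0 | d0 × √50 | Chance of p < .05 |
|---|---|---|---|---|
| 0.10 | 1.5 | 0.067 | 0.47 | .075 |
| 0.10 | 1.0 | 0.100 | 0.71 | .107 |
| 0.20 | 1.5 | 0.133 | 0.94 | .152 |
| 0.20 | 1.0 | 0.200 | 1.41 | .284 |

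The nominal rate is .050. Additions change the picture. With q = 0.20, a = 0.10 and s = 1.0, d0 = (0.20 − 0.10)/1.0 = 0.10 and the rate is .107, not .284. With q = a, d0 = 0 and the rate is the nominal .05. With a > q the mean moves against the hypothesis.

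A larger sample does not help. At d0 = 0.20 the rate is .205 with N = 34 and .284 with N = 50.

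**Hypotheses 3 and 5.** Suppose 20% have a recently started drug with a remaining response of 0.5 to 0.8 SD of change. The mean shift is 0.20 × 0.5 = 0.10 SD to 0.20 × 0.8 = 0.16 SD. At N = 50 the chance of p < .05 is .107 to .199.

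**Would agreement in direction be a sufficient check?** One might claim benefit only if the analysis without recent changers points the same way. I simulated N = 50 with no assay effect and 10 participants carrying a 0.5 or 0.8 SD shift (400,000 runs each). Favourable significant results occurred in 9.6% and 17.1% of runs. Of these, 99.99% and 99.8% still pointed the same way after those 10 were dropped. The other 40 participants largely determine the full-sample mean, so the rule screens out almost nothing.

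**The case against.** The strongest reply has four parts.

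1. **The protocol already limits attribution.** A within-group t-test tests for change, not cause, and 5.6 names the missing control group as the main limitation. This stands against any reading that the plan formally credits these changes to the assay. But the caveat is general and alters no analysis, and the same paragraph expects the results to show whether the assay and G-DIG are beneficial.

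2. **The entry wording looks forward.** A provider who thinks a change is warranted has probably not yet made it, and 5.3 expects some changes to be held back during consent. This makes entry in mid-change less likely. It is not a rule, and it does not cover changes already ordered.

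3. **The pre-result plan captures intended changes.** It may list a taper in progress, and comparing week 12 with it would deal with usual-care change more broadly than a look-back at pre-consent orders. This stands and is taken into the fix. As written, the differences are only noted, 5.6 does not use the plan for the count, and it cannot correct symptom scores.

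4. **The size is assumed throughout.** This stands. The 28% is the extreme corner of the range, and the opposite corner is 7.5%.

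A reader might infer that changes under way push every hypothesis in the favourable direction. The documents do not support that for drug count, because additions ordered before consent raise the week-12 count and nothing shows which kind is more common.

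**Conclusion.** The point holds as an identifiable source of bias of unknown size. Sections 5.4 to 5.6 have no step that finds medication changes ordered before consent, and the planned tests include them in the change. For hypothesis 1 the net direction is open. For hypotheses 3 and 5 the mechanism described, late response to a drug just started, is favourable.

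The rejection rates of 7.5% to 28% (drug count) and 11% to 20% (symptoms) rest on no true effect, N = 50, a two-sided .05 test, the assumed shares and SDs, and no offsetting additions in the drug-count case. They show what could happen, not what will.

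Two stronger readings are not supported. The documents do not show that a positive result would be an artefact of earlier changes. Nor do they show that the sample size is wrong, since N = 34 reproduces. The point is worth acting on because the data needed come from a chart review that is already planned.

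**What to change.** - **Section 5.5, baseline chart review.** Record for each drug the start date, the date of the last change, and any start, stop or taper ordered before consent.
- **Section 5.6, hypothesis 1.** Leave out of the change in count both stops and additions ordered before consent. Treating stops alone would replace one bias with the opposite one. Also report the week-12 regimen against the provider's pre-result initial plan.
- **Section 5.6, hypotheses 3 and 5.** Also report the estimate and 95% confidence interval without participants who had a mental-health drug started, stopped or changed in dose within a pre-specified window before baseline. Four weeks is one example; it is an analysis definition, not an entry or treatment rule. If the estimate shrinks materially, attribute benefit with caution. Do not rely on agreement in direction as the test.

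**Cost.** A few extra chart fields per drug, for five or more drugs per participant, and one supportive analysis with a wider interval. If 10 of 50 are left out, the interval widens by a factor of about √(50/40) = 1.12. Eligibility, visits and treatment do not change. The fix removes only this part of the bias; the general limit of having no control group remains.

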5.5 Study Evaluations

Measures:

The primary measure to determine clinical effectiveness is the Clinical Global Improvement Scale. This scale will be completed both by the provider and the study coordinator (or study personnel collecting the assessment measures).

The number of medications and treatment utilization will be collected by chart review of the subject's medical record at baseline and at 12 weeks to determine any change in the number and type of medications prescribed.

Any differences between the initial medication plan developed by the provider prior to receiving the pharmacogenetic assay results, the medication optimization plan developed by the provider after the use of the G-DIG tool, and actual clinical practice will be noted. The number and cost of medication changes will also be evaluated.

Participant assessments administered at baseline, 6 and 12 weeks will include measures from the Behavioral Health Lab (BHL; Oslin et al., 2006). These measures will include a demographic questionnaire, GAD-7 (Anxiety), PHQ-9 (Depression), PCL-5 (PTSD), Insomnia Severity Index, Chronic Pain, Screening for Alcohol and Drug use, RAND Health Survey, and Side Effects and Adherence (See Appendix A). The results of the BHL assessments will be placed into the subject's medical record. Participants will also be asked about smoking.

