of which 12 code for pharmacodynamic proteins, e.g., receptors, transporters, enzymes, and ion channels. The remaining 6 genes code for pharmacokinetic variants, i.e., CYP450 alleles. Using a proprietary algorithm based on clinical data, the Assay suggests treatment options which might be more or less appropriate for the specific combination of genotype and indication. A naturalistic study of the use of this assay found that 87% of patients demonstrated clinical improvement as measured by the Clinical Global Impression Scale (CGI). Patients also showed decreases in depression, anxiety, and medical side effects, along with increases in their quality of life (Brennan et al., 2014). A recent systematic review of pharmacogenetic testing for the treatment of depression found that overall there was clinical benefit associated with the pharmacogenetic testing, but results for cost effectiveness were mixed (Rosenblat et al., 2017).

In addition to the Genecept® Assay, Genomind has developed the Genomind Drug Interaction Guide (G-DIG), which examines drug-drug-gene interactions. This computerized decision tool for medication providers, uses the genetic information from the Genecept® Assay to look at the current medications being utilized to determine if there are specific drug-drug interactions that may be relevant given the individuals specific genetic test results. This tool allows providers to not only identify medications that are not recommended based on their individual genetics, but also drug-drug interactions that may become problematic. Thus, this tool provides valuable information to providers in order to develop an optimized medication plan.

In summary, polypharmacy is associated with risks of drug-drug interactions, adverse side effects, with unproven clinical benefit. Pharmacogenetic testing may be able to predict an individual's response to medications based on their individual genetic results, which may be beneficial in reducing polypharmacy by eliminating medications that are not beneficial, leading to medication optimization. These pharmacogenetic assays are new to the market and have limited research data. The use of this assay to reduce polypharmacy has never been tested.

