3.0 Objectives

The use of polypharmacy in Veterans, especially for the treatment of PTSD and traumatic brain injury, has increased over the past two decades, exposing Veterans to risks for drug-drug interactions and adverse side effects. Use of a pharmacogenetic tool that could give providers essential information needed to optimize Veteran's medication regimen has the potential to improve Veteran health outcomes, reduce risks for adverse events, and reduce treatment utilization costs.

This project is designed to evaluate the effectiveness of pharmacogenetic testing in individuals who are prescribed psychiatric polypharmacy. The study will test the following hypotheses:

- Use of pharmacogenetic testing and the G-DIG will reduce psychiatric polypharmacy.
- Use of pharmacogenetic testing and the G-DIG information provided to providers will result in changes to the medication treatment plan based on the new information.
- Use of pharmacogenetic testing and the G-DIG will improve overall clinical symptoms as measured by the CGI (secondary analyses).
- Pharmacogenetic testing and the G-DIG will reduce healthcare costs associated with medications (secondary analyses).
- Pharmacogenetic testing will reduce clinical symptoms of anxiety and depression and improve quality of life (secondary analyses).

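### Plans are compared before and after the test result but never with the drug-level result itself, so the second hypothesis is not tested as worded

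*Combined protocol and SAP*

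**What the plan says.** The second hypothesis, in the Abstract and in 3.0, is that giving providers the test and G-DIG information "will result in changes to the medication treatment plan based on the new information".

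That information concerns particular drugs. According to 2.0, "the Assay suggests treatment options which might be more or less appropriate for the specific combination of genotype and indication", and the G-DIG checks the patient's current medications for interactions in light of the genotype. Under 5.1, a drug missing from the G-DIG is to be added to it.

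The planned evaluation is in 5.5. It refers to "Any differences between the initial medication plan developed by the provider prior to receiving the pharmacogenetic assay results, the medication optimization plan" and continues "developed by the provider after the use of the G-DIG tool, and actual clinical practice will be noted". It adds "The number and cost of medication changes will also be evaluated", and a chart review at baseline and week 12 "to determine any change in the number and type of medications prescribed". Section 5.6 then states "The primary and secondary hypotheses will be calculated using within group t-tests". It also concedes that "there is no control group, so attribution of any change to the pharmacogenetic assay should be done with reservations".

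Assay content is recorded in only one place: 5.1 has recommended drugs that are off formulary noted, with no analysis attached.

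**The concern.** The hypothesis has two parts: plans change, and the new information is the reason. The planned data address the first part. For the second they show only the order of events, because the content of the result is never set against the change.

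The protocol itself supplies other reasons for a plan to change:

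- Inclusion criterion 2 (5.4) admits only patients whose provider already judges a medication change to be warranted.
- Consultation with the sponsor is compulsory for each provider's first two subjects (5.1).
- Time passes between the two plans and before implementation (5.1).

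A change that contradicts the report is recorded in the same way as one that follows it. Section 5.1 lists poor advice from the assay as a risk. That risk cannot be examined without knowing which changes followed the advice.

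**Working it through.** **1. The plan's own figure.** Inputs from 5.6: effect size d = 0.50, alpha .05, power 0.80, single-sample t-test. Using the noncentral t distribution with noncentrality d√n and a two-sided test, n = 33.4, which rounds up to 34. This matches the stated N. At n = 34 the power is 0.808. At N = 50 it is 0.934, and the smallest d detectable with 80% power is 0.404. These figures concern a mean within-patient change. They say nothing about agreement with the assay.

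**2. What the planned comparison separates.** As an illustration, take a patient on drugs A to E whose report marks only A as less appropriate.

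| Pre-result plan | Post-result plan | What 5.5 records | Agrees with report? |
|---|---|---|---|
| No change | A stopped | One difference, one drug fewer | Yes |
| No change | B stopped, A kept | One difference, one drug fewer | No |
| B stopped | B stopped | No plan difference | Not applicable |

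Row 3 shows what the design does well: a change already intended before the result is not credited to it. Rows 1 and 2 look the same by count of differences, although only row 1 fits the hypothesis as worded.

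**3. Whether the missing comparison is feasible.** Results sit on the clinician portal (5.1) and are kept indefinitely (7.0, 9.0). Study staff already review the record after the week-12 assessment (5.1). With 50 patients on at least 5 drugs each (5.4), there are at least 50 × 5 = 250 drug entries.

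**4. What a flagged-versus-unflagged contrast could detect.** The documents give no flag rate or change rate, so everything in this step is assumed.

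*Unpaired approximation.* Suppose 20% of 250 drugs are flagged, giving 50 against 200. The detectable arcsine difference is h = (1.960 + 0.842) × √(1/50 + 1/200) = 2.802 × 0.158 = 0.443. The detectable flagged rate is sin²(arcsin√p + h/2), where p is the unflagged rate.

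- p = 10%: 26.7%, or 31.2% with a design effect of 1.5 (h × √1.5).
- p = 20%: 40.0%, or 45.0% with the same design effect.

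*Paired simulation.* The approximation does not match a within-patient analysis, so the contrast was also simulated (3,000 runs per cell). The test was a paired t-test on each patient's flagged-minus-unflagged proportion changed. Assumptions: N = 50, 5 drugs per patient, 20% of unflagged drugs changed, patient random-effect SD 0.5 on the logit scale, two-sided .05. Each cell gives power with 1 / 2 flagged drugs per patient.

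| Patients with both kinds of drug | Flagged changed 30% | 40% | 50% |
|---|---|---|---|
| 50% | 0.119 / 0.206 | 0.416 / 0.615 | 0.732 / 0.912 |
| 75% | 0.191 / 0.318 | 0.601 / 0.800 | 0.906 / 0.985 |
| 100% | 0.258 / 0.391 | 0.765 / 0.910 | 0.969 / 0.998 |

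With 40 completers and 40% of flagged drugs changed, power runs from 0.323 to 0.831. A 10-point contrast is out of reach. A 20-point contrast reaches 80% only in the more favourable cells, and a 30-point contrast reaches it in most.

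**The case against.** The strongest reply is that the protocol already has a within-patient comparison aimed at this hypothesis. The provider writes an optimization plan before seeing the result and a revised one afterwards, for the same patient. Because the first plan is itself a medication review, the difference between plans removes part of any generic review effect. Section 5.6 also cautions on attribution and calls for a randomized control group in future work. All of this stands.

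It rules out several stronger readings that a reader might infer:

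- **That the trial can say nothing about the second hypothesis, or has no within-patient comparison.** The two-plan comparison gives real, if incomplete, evidence. What remains unseparated is second thoughts, elapsed time and the compulsory consultation.
- **That the opportunity is lost.** The results are retained. The analysis is only not pre-specified.
- **That flag status is an internal control, so the assay earns credit only if flagged drugs change more often.** Flags are not random across drugs. They may cluster in psychiatric drugs, which a mental health provider may change more often anyway. An interaction flag concerns a pair, so an assay-driven change may fall on the other member, and a suggested alternative may replace an unflagged drug. Equal rates would therefore not show that the assay had no influence, and at this sample size a null result would be weak evidence.

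The reply does not touch the narrower point: no planned evaluation sets a change beside the drug-level result.

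**Conclusion.** The point holds in a limited form. The trial can show that plans changed after testing, but as planned it cannot show that the changes agreed with the test, which the second hypothesis asserts. This rests on reading 5.1, 5.5 and 5.6 together and not on any power figure; the sample-size calculation is correct for what it covers.

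The remedy is a cheap improvement to the protocol. It has limits. Agreement is weaker than causation, since some changes will match the report by chance. It shows uptake of the result and not clinical benefit. A formal flagged-versus-unflagged comparison would detect only a large contrast at N = 50, roughly 20 to 30 points, and that range depends entirely on the assumed flag and change rates.

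**What to change.** **In 5.5.** At the chart review after the week-12 call, abstract the Genecept/G-DIG category for each drug on the list when the result was reviewed and for each drug added later. Define the categories in advance. Count both members of a flagged interaction pair, and count assay-suggested substitutions.

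**In 5.6, for the second hypothesis.** Count a change as based on the result only if it is absent from the pre-result plan and concordant with the result. Report the number per patient and the proportion of such changes with confidence intervals, separately for the optimized plan and for week-12 practice. State how patients with no new change enter the proportion.

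**Supportive and descriptive only.** Report the within-patient difference in change rates between flagged and unflagged drugs with a confidence interval, clustered on patient and restricted to or stratified by mental-health drugs. This gives some sense of how much agreement would arise anyway. Attach no pass/fail rule. State that concordance measures uptake and that only a large contrast is detectable.

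If the sponsor does not want this, the alternative is to delete the clause about the new information from the hypothesis.

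**Cost.** Abstraction of about 250 or more drug entries from existing reports, one added analysis, and linkage of the assay ID to the separate study ID. The linkage and abstraction should wait until the subject's blinded calls are complete, so that raters stay blind. No extra patient contact is needed.
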